targeting both amyloid and tau, there is a huge need to understand tau burden among Mexican Americans. Prior work by our team, and others, has shown that when compared to non-Hispanic whites, Mexican Americans (1) are at increased risk for MCI and AD⁶, (2) are diagnosed at a more advanced stages of disease progression^{3,8} (3) develop MCI and AD at younger ages^{2,8,12}, (4) have a lower frequency of the ApoE ϵ 4 allele^{2,3,16}, (5) suffer from a disproportionate burden of modifiable risk factors for MCI and AD (e.g. diabetes, depression)^{2,3,17} and (6) demonstrate an AD proteomic profile that is metabolic in nature¹⁸. In our HABLE-Amyloid pilot project, we now have data showing that amyloid burden among Mexican Americans that have been clinically diagnosed as MCI or AD (1) have significantly lower amyloid burden as compared to non-Hispanic whites; however, they also (2) have comparable levels of neurodegeneration as measured by plasma NfL levels. Therefore, our data demonstrates medical, genetic, proteomic and amyloid differences among Mexican Americans diagnosed with MCI and AD as compared to non-Hispanic whites. In fact, we have identified cognitive loss at younger ages that is associated with neurodegeneration in the absence of amyloid among Mexican Americans. Given that tau is associated with global neurodegeneration, it is possible that Mexican Americans are suffering altered levels of tau burden when compared to non-Hispanic whites. This also suggests that the “accepted” sequence of pathological burden could be fundamentally different among this population. However to date no studies are examining Tau burden via PET scan in Mexican Americans. Moreover, questions remain regarding the feasibility of recruiting this population into Tau research studies.

This study seeks to address this gap through the achievement of the following specific aims: 1) Conduct a pilot study regarding the feasibility of recruiting Mexican Americans with known amyloid status into a PET tau scan study, 2) Examine the prevalence of tau burden among community-dwelling Mexican Americans suffering with known amyloid burden.

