All participants will be injected with a 370 MBq (10 mCi) bolus of Flortaucipir (¹⁸F), ¹⁸F-AV-1451(¹⁸F-T807). Up to 90 min post injection the participants will be positioned on the imaging table of a Siemens ECAT HR PET scanner. Soft Velcro straps and foam wedges will be used to secure the participant's head and the participant will be positioned using laser guides. A 2min scout will be acquired to ensure the participant's brain is completely in the field-of-view and there is no rotation in either plane. A 2-frame by 5-min each dynamic emission acquisition will be started up to 90min post injection and immediately after a Ge-68/68-Ga source transmission scan is acquired for 7min. The transmission image will be reconstructed using back-projection and a 6mm FWHM Gaussian filter. The emission images will be processed by iterative reconstruction, 4 iterations and 16 subsets with a 3mm FWHM ramp filter. Images will be reconstructed immediately after the 10-minute scan, and if any motion is detected, another 10 minute continuous scan will be acquired.

Time: The PET scan may take up to 120 minutes, not including travel to and from the facility.

Risks

The total radiation exposure from Flortaucipir administration and subsequent PET scan is estimated to be 8.70mSv. The amount of radiation exposure is equivalent to an additional year's worth of radiation exposure experienced by individuals in the US (clinical procedures, food, environment, etc.). Because the doses of radiotracers administered are small, diagnostic nuclear medicine procedures result in relatively low radiation exposure to the participant, acceptable for diagnostic exams. The most common adverse reactions to Flortaucipir reported in the Investigational Brochure (n=273) were injection headache (2.2%), diarrhea (1.1%), hypertension (0.7%) and muscle spasms (0.7%). All others reported were <0.5% (musculoskeletal discomfort, dysgeusia, nausea, oral pain, bronchial secretion retention, epistaxis, injection site pain, dizziness, flushing, fatigue, hypotension, feeling cold, insomnia). All were reported as mild or moderate severity and all subjects recovered. Back and neck pain may be experienced from lying in the scanner. No consistent or clinically relevant changes in vital signs, laboratory values or ECG results have been observed in completed studies. Additional risks associated with this protocol are discussed in detail in the Risks/benefits section.

Feedback

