Given that Flortaucipir is not FDA approved, tau cerebral burden will not be provided back to participants at this time. If Flortaucipir (1) becomes FDA approved and (2) clinical guidance's are provided for healthcare providers, we will modify the protocol at that time. If new information is released regarding Flortaucipir during the study, we will give it to the participants.

2) Data Analysis and Data Monitoring -

As with all Health and Aging Brain Study neuroimaging protocols (MRI, PET), all images will be directly uploaded, stored and analyzed at USC/LONI per ADNI protocols. USC/LONI has well-established protocols for analyzing cerebral tau PET scans from 1,000s of scans. All research data will be managed by our research team and stored in the Institute for Translational Research (ITR) Data Core. Periodic Quality Control checks will be conducted by our personnel and provided to the PI. All electronic records will be maintained on password protected computers behind locked doors in the ITR office space. All files will be backed up weekly, again located in the ITR office space. After data is entered the database will be transferred to the Institutional server, which will afford additional safeguards and backup. This study will enroll up to 40 Mexican Americans currently enrolled in the Health and Aging Brain Study: Health Disparities Amyloid Project (2017-165).

Standard clinical labs work will be conducted by Quest diagnostics. Samples will be labeled with a participant's medical ID number. This number is generated by the research team and is different from the participants research ID.

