PET Data Processing. All PET scan images will be uploaded to the LONI server and analyzed by LONI personnel. We will perform the following processing of the scans: 1) Co-registration of frames to correct for motion; 2) Creation of an average image (90-110 min p.i.); and 3) Co-registration of the average image to the individual SPGRs (T1-weighted MRI). We will use FreeSurfer to segment the native space SPGR scan to obtain masks for whole cerebellum and four cortical regions of interest: frontal, anterior/posterior cingulate, lateral parietal, and lateral temporal cortices. We will intensity-normalize the PET images using mean PET signal in the whole cerebellum as a reference region, consistent with the standard ADNI protocol for cross-sectional studies. The global standardized uptake value ratio (SUVR) will be equal to the mean PET signal in the cortical regions of interest divided by mean signal in the whole cerebellum. We will also calculate regional SUVRs in each of the lobes, and in FreeSurfer-derived orbitofrontal, anterior and posterior cingulate

cortices, and precuneus.

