The Master Linking File will be a separate password-protected file maintained by authorized research personnel. This file will hold the link between the research ID numbers and individually identifying information on each participant. Only authorized research personnel will have access to this file. This linking file will enable accurate tracking of research participants across multiple visits. Each participant has a Medical ID number assigned.

The imaging facility may require the participant name, date of birth, and medical ID number to complete research scans. This protocol is in place for safety and insurance purposes to protect the participant as well as the radiologists and center. To protect confidentiality the site will de-identify the results of the scan (using the medical id number), which will make it impossible to connect the participant's name to the findings. Additionally, the imaging facility will not be provided with the participant's research id number.

See diagram below.

This study has a Certificate of Confidentiality from the National Institutes of Health.

4) *Setting* - Describe briefly where the study will be conducted, e.g., private outpatient clinics, physicians' offices.

Participants will be seen in the Health and Aging Brain Study offices in the Institute for Translational Research for the consenting and medical exam and ECG. They will go to the clinical laboratories for the blood draw (Quest), and then they may be accompanied by a member of the research team to the imaging center for the brain scans. The particular center will depend on availability of scanners.

Since we may contract with multiple imaging sites we will submit an addendum for each site that outlines the site specific requirements for research and a copy of the requisition forms.

5) *Laboratory methods and facilities* –

As outlined above, each study participant will undergo brain PET scan at an imaging center. The imaging center(s) will conduct the scans as a fee-for-services contract, similar to the process we already have in place where Quest Diagnostics (or another lab) conducts clinical labs for our research participants. See Procedures Section above for description of imaging procedures to be completed.

6) *Estimated Period of Time to Complete the Study* – Rough estimates of the time can be found below:

Consent and screening visit: 30 minutes -1 hour
 PET Scan: up to 120 minutes

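### The protocol acquires a 10-minute PET emission scan but defines the image behind the tau SUVRs over a 20-minute window, and sets no earliest start for the scan

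*Protocol*

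**What the plan says.** **Acquisition (Protocol E.1, Methods and Procedures, PET scan, Procedure).** The emission scan is described as follows: "A 2-frame by 5-min each dynamic emission acquisition will be started up to 90min post injection". The same paragraph confirms the length and adds a conditional repeat: "Images will be reconstructed immediately after the 10-minute scan, and if any motion is detected, another 10 minute continuous scan will be acquired". It also describes a 7-minute transmission scan, which yields no emission data.

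**Processing (Protocol E.2, PET Data Processing).** The second processing step reads "Creation of an average image (90-110 min p.i".). The steps that follow are co-registration to the T1-weighted MRI, normalisation to the whole cerebellum, and calculation of a global SUVR and regional SUVRs. No other image is described as their source.

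**Related text.** E.2 says that "all images will be directly uploaded, stored and analyzed at USC/LONI per ADNI protocols", without giving an acquisition window under that heading. E.4 (Setting) expects more than one imaging centre: "The particular center will depend on availability of scanners", and "Since we may contract with multiple imaging sites we will submit an addendum for each site". Aim 2 in section A is to "Examine the prevalence of tau burden among community-dwelling Mexican Americans" with known amyloid burden.

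**The concern.** The two sections give incompatible instructions for the same measurement. The imaging centre is told to collect 10 minutes of emission data; the processing team is told to average over 20. Processing can impose one averaging rule on every scan, but it cannot recover minutes that were not acquired. Frames from a scan started at 90 minutes can still be averaged, but the result is a 90–100 minute SUVR and not the 90–110 minute SUVR that the protocol defines.

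The start time adds a second weakness. The words "dynamic emission acquisition will be started up to 90min post injection" set a latest start and no earliest one. Read literally, a scan that complies with E.1 could lie partly or wholly before the window in E.2. Since scans may be made at several centres, the post-injection interval behind the SUVR could then differ from one participant to the next.

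What is at stake is aim 2. The SUVRs are the only tau measures the protocol describes, and any statement about the prevalence of tau burden rests on them.

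**Working it through.** **Inputs**

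- Emission frames: 2, of 5 minutes each (E.1, Procedure).
- Latest emission start: 90 minutes post injection; no earliest start (E.1, Procedure).
- Averaging window: 90 to 110 minutes post injection (E.2, PET Data Processing).
- Transmission scan: 7 minutes (E.1, Procedure).
- Repeat emission scan: 10 minutes, only if motion is detected (E.1, Procedure).

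**Length.** Acquired: 2 × 5 = 10 minutes, which reproduces the protocol's own description of the scan as lasting 10 minutes. Stated window: 110 − 90 = 20 minutes. At the E.1 frame length the window would hold 20 / 5 = 4 frames, against 2 acquired.

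**Overlap.** For a routine scan started at *s* minutes, running to *s* + 10:

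overlap = max(0, min(*s* + 10, 110) − max(*s*, 90)).

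This equals 10 for 90 ≤ *s* ≤ 100 and is smaller for every other *s*. So no start time gives more than 10 / 20 = 50%.

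For starts that E.1 allows (*s* ≤ 90):

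| Emission start (min) | Emission end (min) | Minutes inside 90–110 | Share of 20 |
|---|---|---|---|
| 90 | 100 | 10 | 50% |
| 85 | 95 | 5 | 25% |
| 80 | 90 | 0 | 0% |

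Because *s* + 10 ≤ 100, the overlap with minutes 100–110 is 0 in every row. The scan midpoint is *s* + 5 ≤ 95 minutes, against (90 + 110) / 2 = 100 for the stated window. The rows below 90 minutes show what the wording permits, not what is known to happen.

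**Does the motion repeat fill the window?** Take a start at 90 minutes.

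- Repeat with no gap: it runs 100–110, so coverage is 10 + 10 = 20 of 20 minutes.
- Repeat after the 7-minute transmission scan: it runs 107–117, of which 107–110 counts, so coverage is 10 + 3 = 13 of 20 minutes.

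In both cases the first 10 minutes are the motion-affected data, and participants without motion have no repeat at all.

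**Does the visit time settle which length was meant?** The PET visit is stated as up to 120 minutes. If that includes the wait after injection, 90 + 10 + 7 = 107 and 90 + 20 + 7 = 117 both fit, so it does not decide the matter.

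**The case against.** The strongest reply is that the 90–110 minute figure is a bracket within which whatever frames exist are averaged, not a promise of 20 continuous minutes. A scan from 90 minutes plus an immediate motion repeat would span exactly that bracket. On this reading the fault is loose wording and no data are missing. But E.2 does not say this, and the match depends on a conditional repeat with no transmission scan in between. Even if it were right, the text would still misstate the window for every participant without a repeat.

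Second, the limit on the start time may simply be an imprecise way of saying about 90 minutes. The same phrase is used for positioning the participant on the table, and the E.2 window opens at 90. That is plausible, and it is why early starts are treated here as permitted but not shown to occur. If all scans do start near 90 minutes, participants remain comparable with one another and the measure is mainly mislabelled.

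Third, the addenda promised in E.4 are to set out site-specific requirements and might fix scan timing. They are not available here, so this can be neither relied on nor excluded. Nothing shows that sites would in fact use different intervals. The mismatch between E.1 and E.2 exists within the protocol itself in any case.

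Finally, no effect on any result has been demonstrated. That is true, and it limits how serious the point is.

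**Conclusion.** The inconsistency is real and should be corrected. A routine scan as specified supplies at most 10 of the 20 minutes in the stated averaging window, that is 2 of 4 five-minute frames, and with a start at or before 90 minutes it supplies none of minutes 100–110. This follows from the protocol's own figures and needs no outside assumption.

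Two further statements are conditional. That every SUVR derives from the averaged image is inferred from the order of the processing steps, since no other source is described. That the post-injection interval varies between participants requires scans to start at different times, which the wording allows but nothing confirms.

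The effect on SUVR values, and so on aim 2, cannot be quantified from the protocol. Aim 1 is untouched, and aim 2 is descriptive in up to 40 participants. The correction is nonetheless worth making before scanning, because unacquired minutes cannot be recovered afterwards.

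**What to change.** Reconcile the PET Procedure in E.1 with PET Data Processing in E.2 so that both give one acquisition and averaging window. The protocol does not show which was intended, so the sponsor must decide.

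- If the 10-minute scan is kept, change the averaging window in E.2 to the interval actually acquired.
- If the 90–110 minute window is kept, E.1 must acquire all of it.

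In either case, replace the open-ended emission start with a stated start time and a tolerance that apply at every imaging centre, so that each participant's SUVR comes from the same post-injection interval.

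The cost is a wording change in two sections and a note to the imaging centres and the processing team. Keeping the 20-minute window adds 10 minutes of emission scanning per participant. In that case a motion repeat would give 90 + 20 + 7 + 10 = 127 minutes, so the stated limit of 120 minutes would also need review if it counts the wait after injection.

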The current study is **highly significant** for several reasons: (1) this is the first-ever study of the tau hypothesis among Mexican Americans; (2) this study will examine how tau is potentially differentially present among Mexican Americans; (3) this study will demonstrate, for the first time, the feasibility of recruiting Mexican Americans into a PET tau scan study.

B. Background and Significance -

The long-term goal of this research is the generation and validation of biomarkers of Alzheimer’s disease (AD) among Mexican Americans. Despite the rapidly growing Mexican American elderly population, little research has been conducted on AD among this ethnic minority group. Research that has been conducted suggests that a significant health disparity exists with Mexican Americans (1) being at increased risk for AD, (2) being diagnosed with AD at younger ages and more advanced stages, (3) experiencing significantly longer disease duration as well as delays in diagnosis and treatment, and (4) being misdiagnosed due to invalid/inaccurate measures. The 2018 AT/N Framework has now provided a biologically-based system for examining the emergence and progression of AD; however, all of the data in support of this framework is based on non-Hispanic whites. This means that our fundamental understanding of the pathological processes underlying AD is not reflective of our diverse U.S. population. Additionally, the research underlying our conceptualization is based on clinic-based samples, which are substantially biased. Therefore, here we will conduct a pilot study of cerebral tau burden among Mexican Americans with known amyloid status to set the stage for a large-scale community-based study of the 2018 AT/N Framework among a diverse cohort.

A tremendous amount of progress in neuroimaging biomarkers of AD has been accomplished within the last decade, which is largely due to the Alzheimer’s Disease Neuroimaging Initiative (ADNI), the most

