The Health and Aging Brain Study HD: Amyloid Project (2017-165) is currently recruiting up to 1000 participants from the Health and Aging Brain Study HD: Health Disparities (2016-128) to undergo amyloid PET scans. All other research components are captured as part of the parent IRB protocol. Here, we propose to re-contact n=40 participants who self-identify as Mexican American, that have already undergone amyloid PET scans as part of IRB 2017-165, and have given permission for re-contact.

Participants will be re-contacted using the **Recruitment Script (see attachment)**. Please note that the script for this study is minimal. Our team has extensive experience recruiting older underserved individuals

into research. We have found our participants prefer to have discussions face to face rather than over the phone. Additionally, during the amyloid study, we informed participants of the potential for another PET scan study in the future.

For those individuals who wish to participate, an appointment will be set up for him/her to come to our research offices for an in-person visit to conduct the consent and screening visit. This can take place in one visit or spread out over multiple visits. The study doctor will review the information collected in the medical exam and determine eligibility.

If the participant meets eligibility criteria, the research team will schedule an appointment for the participant to receive the brain scan at an imaging center. Participants will undergo a PET scan. Participants will be screened by the research team during the medical exam, and by the imaging center staff before they are scanned. The imaging center personnel will carry out their standard/internal procedures for verifying PET scan eligibility. If the imaging center identifies a safety concern they will notify the research team.

Participants unable to undergo a scan will be withdrawn from the study by the research team. The participants may meet a member of the research team at the imaging facility on the day of the scan.

Participants must complete the PET scan in order to be compensated for his/her time.

The data collected in this study will be linked with the participant's data collected in The Health and Aging Brain Study HD: Health Disparities IRB# 2016-128 and The Health and Aging Brain Study: Health Disparities Amyloid Project IRB# 2017-165.

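### The tau composite and the listed regional SUVRs name no medial temporal region, so tau confined there would tend to be missed if Aim 2 prevalence were judged on the composite

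*Protocol*

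**What the plan says.** Section A (Specific Aims) sets Aim 2 as follows: "Examine the prevalence of tau burden among community-dwelling Mexican Americans suffering with known amyloid burden". The same section raises the possibility that the accepted "sequence of pathological burden could be fundamentally different among this population", and gives as one reason for the study's significance that "this study will examine how tau is potentially differentially present among Mexican Americans".

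Section E.2 (PET Data Processing) fixes how tau is to be measured. FreeSurfer is to supply masks for the whole cerebellum and for "four cortical regions of interest: frontal, anterior/posterior cingulate, lateral parietal, and lateral temporal cortices". The summary measure follows from these masks: "The global standardized uptake value ratio (SUVR) will be equal to the mean PET signal in the cortical regions of interest", divided by the cerebellar mean. The plan then adds: "We will also calculate regional SUVRs in each of the lobes, and in FreeSurfer-derived orbitofrontal, anterior and posterior cingulate" cortex, and precuneus.

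The opening of E.2 says in general terms that images will be "stored and analyzed at USC/LONI per ADNI protocols", and that the imaging laboratory has established procedures for tau PET. It names no region.

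The protocol ties no particular SUVR and no cut-off to Aim 2. That may be settled in the statistical analysis plan, which is not at hand, and it is not the point here.

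**The concern.** The temporal part of the composite is expressly lateral. Below the level of whole lobes, the regional list gives detail for orbitofrontal cortex, cingulate and precuneus, but none for the temporal lobe. Entorhinal, parahippocampal and hippocampal cortex and the amygdala are not mentioned anywhere in the protocol.

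This fits poorly with what the study wants to learn. Aim 2 asks how often tau is present. Section A also asks whether tau is differently distributed and whether pathology follows a different order in this population, and both depend on where the tau lies. If Alzheimer-type tau often appears early in medial temporal cortex (an assumption; the protocol does not discuss where tau starts), the listed measures are least sensitive where early tau would be found.

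At stake is a downward bias in Aim 2 prevalence if it were judged on the composite. Section B presents the pilot as groundwork for a large community-based study, so the choice of measure could be carried forward.

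**Working it through.** The protocol gives no figure on this point to reproduce: no cut-off, SD, expected prevalence or precision target. The check is a reading of the region list, followed by simple arithmetic.

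**Step 1. What each listed measure contains (E.2, PET Data Processing).**

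| Measure | Medial temporal content |
|---|---|
| Global SUVR | None named; the temporal part is lateral only |
| Lobar SUVRs | A temporal-lobe value is implied; it may include medial tissue, averaged with the rest of the lobe |
| Orbitofrontal, cingulate, precuneus | None |

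**Step 2. How a medial rise passes through.** Let the medial temporal SUVR rise by *d* and nothing else change.

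- Composite: change = (weight of medial tissue) × *d* = 0 × *d* = 0, apart from any spill-over of signal into the neighbouring lateral temporal mask.
- Temporal lobe: change = *m* × *d*, where *m* is the medial share of the lobe mask. With *m* below 1, the rise is diluted. The protocol does not give *m*. Without an SD or a cut-off, no value of *m* would show whether the diluted rise is detected.

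**Step 3. What one missed participant is worth.** The sample size is up to 40 (section F.2).

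- 1/40 = 2.5 percentage points.
- Forty is a ceiling, and "Participants unable to undergo a scan will be withdrawn from the study by the research team" (section E.1). For example, 30 scanned gives 1/30 = 3.3 points and 20 scanned gives 1/20 = 5.0 points. The 30 and 20 are examples only.

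**Step 4. Illustration, all inputs assumed.** Let *p* be the true prevalence and *q* the share of tau-positive participants whose tau is confined to medial temporal cortex. Suppose the composite misses all of these. Apparent prevalence = *p* × (1 − *q*), and the number missed of 40 = 40 × *p* × *q*.

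- *p* = 30%, *q* = 10%: 0.30 × 0.90 = 27%; 40 × 0.30 × 0.10 = 1.2 missed.
- *p* = 30%, *q* = 25%: 0.30 × 0.75 = 22.5%; 3 missed.
- *p* = 30%, *q* = 50%: 0.30 × 0.50 = 15%; 6 missed.
- Over *p* from 20% to 50% and the same *q*: from 40 × 0.20 × 0.10 = 0.8 to 40 × 0.50 × 0.50 = 10 missed.

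For comparison, the normal-approximation 95% half-width at *p* = 30% and n = 40 is 1.96 × √(0.30 × 0.70 / 40) = 0.142, about 14 points. These lines show how the bias would work. They do not estimate it for this trial.

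**The case against.** The strongest objection is that the harm hangs on a condition the protocol never states. Nothing ties Aim 2 to the global SUVR, and the analysis plan could choose otherwise. This stands, and the conclusion is conditional for that reason.

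Second, the importance of the medial temporal lobe comes from outside the protocol. That is correct and is labelled as an assumption. It governs how often the gap would matter, not whether the list has one: a region with zero weight cannot register signal confined to it, spill-over apart.

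Third, the list is not said to be exhaustive, and the laboratory's own procedures may output more regions. That is possible, but those procedures cannot be seen here. The one list that the protocol writes out is the one at issue.

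A reader might infer that medial temporal tau will go unmeasured, or that a later analysis would have no medial temporal value to use. The protocol does not support this. A temporal-lobe SUVR is implied, FreeSurfer segmentation is planned, and section E.2 has the imaging laboratory keep the de-identified scans, so the values can be extracted later. What the text lacks is a named, pre-specified medial temporal measure; no data are lost.

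Finally, at n = 40 the sampling error of about 14 points at an assumed 30% prevalence is larger than two of the three losses shown for that prevalence and just below the third. That is fair, but sampling error shrinks in a larger study and a bias from the choice of region does not.

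**Conclusion.** The concern holds in conditional form. The protocol defines one summary tau measure with no medial temporal component, and its added regional SUVRs name none. If Aim 2 prevalence were judged on the composite, participants whose tau is confined to medial temporal cortex would tend to be missed. That depends on the cut-off, on spill-over and on their other cortical signal.

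The only size that follows from the protocol is 2.5 points per missed participant at n = 40. A reader might infer that prevalence will be understated by some stated amount; the protocol gives nothing from which to derive one. Participants may have Alzheimer's disease (section F.4), and those with tau in the four cortical regions could still register on the composite, so any under-count depends on case mix.

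The conclusion rests on one outside assumption, early medial temporal tau. It merits a change because the plan states a list that fits its own questions poorly and a better list is easily had. Confidence is medium.

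**What to change.** In section E.2, PET Data Processing, add a separately reported medial temporal SUVR (for example entorhinal, parahippocampal and amygdala) taken from the FreeSurfer segmentation already planned. State, before results are seen, that tau burden under Aim 2 will be reported on this measure alongside the global SUVR.

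The cost is about one paragraph of text, a few more output columns from the imaging laboratory and one more pre-specified measure. Two figures will then stand side by side. Small regions are noisier and open to spill-in from neighbouring tissue, so the new measure should supplement the global SUVR and not replace it. No participants, scans or radiation are added, and scans already acquired can be re-extracted.
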